**Primary objective:**

- Comparison of the quantitative proportion of hemo/myoglobin and collagen signal in muscle tissue of healthy subjects before and after physical exercise (6-MWT) determined by MSOT, as well as over time.

**Secondary objectives:**

- Comparison of the quantitative amount of hemo/myoglobin and collagen signal determined by MSOT in muscle tissue of healthy volunteers at timepoint 1 and timepoint 2 after two weeks
- Comparison of the quantitative proportion of oxygenated/deoxygenated hemo/myoglobin signal in muscle tissue of healthy volunteers at timepoint 1 and timepoint 2 after two weeks
- Comparison of the MSOT-determined quantitative amount of hemo/myoglobin and collagen signal at three muscle positions of two muscles (quadriceps femoris and gastrocnemius)
- Comparison of the quantitative proportion of oxygenated/deoxygenated hemo/myoglobin signal determined by MSOT in three muscle positions of two muscles (quadriceps femoris and gastrocnemius)
- Comparison of the quantitative proportion of hemo/myoglobin and collagen signal determined by MSOT in muscle tissue of healthy female and male volunteers
- Comparison of the quantitative proportion of oxygenated and deoxygenated hemo/myoglobin signals determined by MSOT in muscle tissue of healthy female and male volunteers
- Correlation of the hemo/myoglobin and collagen signal determined with MSOT with the 6-MWT
- Correlation of the oxygenated/deoxygenated hemo/myoglobin signal determined by MSOT with the 6-MWT
- Comparison of the quantitative amount of hemo/myoglobin and collagen signal determined by MSOT between two independent examiners

- Comparison of the quantitative amount of hemo/myoglobin and collagen signal determined by MSOT between two images of one examiner

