## 5. Scientific background

Since 2017, the University Hospital Erlangen (Medical Clinic 1, Pediatric and Adolescent Clinic) has a Multispectral Optoacoustic Tomograph (MSOT) funded by the DFG. This allows non-invasive, quantitative imaging of the composition of target tissues in the non-sedated child, comparable to sonography. This is of particular importance in this patient group.

In MSOT, similar to conventional sonography, a transducer is placed on the skin and instead of sound, energy is supplied to the tissue by means of pulsed laser light. This leads to a constant change of minimal expansions and contractions (thermoelastic expansion) of individual tissue components or molecules. The resulting sound waves can then be detected by the same examination unit. Previous studies have shown that the quantitative determination of hemoglobin can be used to obtain information on blood flow and inflammatory activity in the intestine from patients with Crohn's disease (Waldner, Knieling et al. 2016, Knieling, Neufert et al. 2017) (Waldner 2016, Knieling 2017). In the newly configured device (Acuity Echo, iThera Medical GmbH, Munich, prototype) an extended spectrum of laser light can be used, which ultimately not only enables the detection of haemoglobin and its oxygenation stages, but also the detection of further markers such as collagen and lipid. This principle has already been successfully used in a follow-up study on pediatric patients with Duchenne muscular dystrophy (Regensburger, Fonteyne et al., submitted for publication, ESMI Young Investigator Award 2019).

[figure not shown]
[figure not shown]

Figure 1 - MSOT principle (a), experimental preliminary work (b), and first time representation of collagen *in vivo* (c)

We were able to show by our experimental preliminary work and a large animal pig model that an in vivo quantification of collagen is possible. In the first application of MSOT in children with Duchenne muscular dystrophy, the measured collagen content correlated with the clinical function tests. In summary, we could show that the molecular muscle structure quantified by MSOT allows the establishment of new, age-independent, non-invasive molecular biomarkers for disease assessment and therapy monitoring in patients with DMD.

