## Recording of target parameters

- Non-invasive in-vivo measurement of hemo/myoglobin, collagen and lipid content/signal and oxygenation by MSOT
- Assessment of the 6-minute walk test
- Determination of routine data (height, weight, underlying diseases, medication)

Time schedule and study duration for the individual volunteer:

The duration of the study participation is about 125 minutes for the individual volunteer. At timepoint 1 the duration of study participation is 75 minutes. Approximately 20 minutes are allotted for the education of study participants, approximately 5 minutes for the collection of routine clinical data, 10 minutes for clinical (routine) testing using 6-MWT, and 40 minutes for the actual examination. At timepoint 2, participation time for the study is about 50 minutes. The clinical (routine) test using 6-MWT takes 10 minutes, and 40 minutes for the actual examination.

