#### ***Statistical methods:***

The data are given as mean value with standard deviation. Correlations are specified with the parametric Pearson correlation coefficient (R). According to the distribution between timepoint 1 and timepoint 2, the differences of the mean values are statically examined with a parametric T-test. In all analyses, an error level of <0.05 is considered statically significant.

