Non-invasive molecular imaging to determine the hemoglobin and collagen content in muscles before and after physical exercise and over time (MSOT_muscles)

Unique Protocol ID: 169_19B

ClinicalTrials.gov Identifier: NCT03979157

Version date: 23.04.2019

Sponsor:

Department of Pediatrics and Adolescent Medicine
University Hospital Erlangen
Friedrich-Alexander-University (FAU) Erlangen-Nürnberg
Pediatric Experimental and Translational Imaging Laboratory (PETI-Lab)
[name]
[name]
[contact]

Statistical Analysis Plan

The present study is a pilot proof-of-concept study. Due to lack of clinical trials in this area, the comparative changes of MSOT spectra and signals within and between examiners, before and after exercise, over time and between different muscles and muscle positions are unknown. Therefore, no sample size calculation was performed.

The primary outcome measure is to assess the reproducibility of the muscular optoacoustic spectra of healthy volunteers facing different variables (examiner, time, exercise, muscle position).

MSOT signals are derived from averaged video captures (seven frames) obtained in anatomical independent muscle regions in patients. All anatomical locations are considered independent. In cases of multiple scans/recordings, a mean of all analyzed scans is calculated.

Continuous variables are given as means and standard deviations; categorical variables are provided as numbers and percentages. Data are tested for normal distribution using Shapiro-Wilk test prior to inferential analysis. MSOT signals are compared matched manner using a paired t-test when parametric and a Wilcoxon matched-pair signed rank test when non-parametric. For the comparison of three or more groups analysis of variance (ANOVA) and for nonparametric distribution Friedman Test is used. Correlations are specified with the parametric Pearson correlation coefficient (r) and the nonparametric Spearman correlation (r_s), using a 95% confidence interval. Additionally, the intraclass correlation coefficient (ICC) will be used with the grading proposed by Landis and Koch. For all analysis an error level of $p < 0.05$ is considered as statistically significant. All analyses are performed using GraphPad Prism (Version 8, GraphPad Software, La Jolla, CA, USA) and/or IBM SPSS Statistics (Version 24, IBM Corp., N.Y., USA).

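### The correlations of MSOT signal with the 6-MWT are unadjusted in a sample open to both sexes, so if signal and walk distance both differ by sex, the coefficient can reflect a sex contrast

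*Protocol*

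**What the plan says.** Two secondary objectives in Protocol section 6 relate the imaging signals to the walk test: "Correlation of the hemo/myoglobin and collagen signal determined with MSOT with the 6-MWT" and "Correlation of the oxygenated/deoxygenated hemo/myoglobin signal determined by MSOT with the 6-MWT". Protocol section 12 (Statistical methods) names a Pearson coefficient for correlations and nothing more. The SAP widens this: "Correlations are specified with the parametric Pearson correlation coefficient (r) and the nonparametric Spearman correlation (r_s), using a 95% confidence interval". Neither document names strata, a covariate or a predicted walk distance for this analysis.

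Section 9 admits any adult and plans 10 volunteers, with no sex ratio. The secondary objectives also compare signals "in muscle tissue of healthy female and male volunteers", so both sexes are foreseen and a sex difference in signal is an open question. Gender is among the secondary targets (section 7) and height among the routine data (section 10). Neither is linked to the correlation.

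**The concern.** A correlation across people picks up any stable trait that shifts both variables. The before/after exercise comparison is made within a person, so a fixed trait such as sex drops out of it. The 6-MWT correlation has no such protection. If one sex walks further and also has a higher (or lower) signal, a coefficient over everyone is non-zero even when signal and distance are unrelated within each sex. Sex differences can also offset a real within-sex relation.

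Interpretation is what is at stake. Section 5 cites an earlier result in patients: "In the first application of MSOT in children with Duchenne muscular dystrophy, the measured collagen content correlated with the clinical function tests". It presents this in support of MSOT as a biomarker. A correlation found in the healthy volunteers could be read the same way when it is only a contrast between women and men.

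**Working it through.** The plan gives no expected correlation, power or sex difference, so there is no figure of its own to reproduce.

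**Inputs from the documents:** n = 10 (Protocol section 9); significance at 0.05 (Protocol section 12 and SAP), taken as two-sided because sidedness is not stated; unadjusted coefficients.

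**Assumptions:** one value per volunteer; zero correlation within each sex; normal data; sex differences of d_s (signal) and d_w (walk distance) within-sex SDs, each between 0 and 2; 5/5 and 3/7 sex splits.

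**Step 1, correlation induced by sex.** With p the proportion of one sex and v = p(1−p),

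r = v·d_s·d_w / √[(1 + v·d_s²)(1 + v·d_w²)].

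With d_s = d_w = d this becomes r = v·d² / (1 + v·d²). If either difference is 0, then r = 0.

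- 5/5 split, v = 0.25: d = 0.5 gives 0.0625/1.0625 = 0.06; d = 1 gives 0.25/1.25 = 0.20; d = 1.5 gives 0.5625/1.5625 = 0.36; d = 2 gives 1/2 = 0.50.
- 3/7 split, v = 0.21: 0.0525/1.0525 = 0.05; 0.21/1.21 = 0.17; 0.4725/1.4725 = 0.32; 0.84/1.84 = 0.46.

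**Step 2, critical values.** |r| = t/√(df + t²), with t the two-sided 5% point.

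- Crude, df = 8: 2.306/√(8 + 5.318) = 0.632.
- Partial given sex, df = 7: 2.365/√(7 + 5.591) = 0.666.
- Partial given sex and height, df = 6: 0.707.

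**Step 3, how often p<0.05 is reached with no within-sex relation** (Pearson, 200,000 simulated studies per row):

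| Split | d, signal | d, distance | Crude | Partial given sex |
|---|---|---|---|---|
| 5/5 | 0 | 2 | 5.0% | 5% |
| 5/5 | 0.5 | 0.5 | 5.2% | 5% |
| 5/5 | 0.5 | 1 | 6% | 5% |
| 5/5 | 0.5 | 2 | 7.8% | 5% |
| 5/5 | 1 | 1 | 8.7% | 5% |
| 5/5 | 1 | 2 | 15% | 5% |
| 5/5 | 1.5 | 1.5 | 19% | 5% |
| 5/5 | 2 | 2 | 37% | 5% |
| 3/7 | 1 | 1 | 8% | 5% |
| 3/7 | 1.5 | 1.5 | 16% | 5% |
| 3/7 | 2 | 2 | 30% | 5% |
| 1/9 | 1 | 1 | about 6% | 5% |

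Differences in opposite directions give a negative r of the same size and the same rejection rate.

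**Step 4, precision.** By the Fisher transformation, an observed crude r of 0 has a 95% interval of ±tanh(1.96/√7) = ±0.63. For the partial correlation it is ±tanh(1.96/√6) = ±0.66.

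**Step 5, unit of analysis.** The SAP treats anatomical locations as independent. Suppose that rule is applied here, with an assumed correlation of 0.5 between locations within a person. The crude test then rejects in 24% of studies with 4 locations per person (2 muscles × 2 sides) and 47% with 12 (three positions each), with no sex difference at all. That excess comes from clustering, not sex.

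**The case against.** The strongest reply is that both premises are assumed. The documents give no sex or height difference in distance or signal, none of the hypotheses in section 6 concerns sex, and section 12 says no information on expected group differences exists. A sex difference in distance alone does nothing, and with a signal difference of only 0.5 SD the rate is at most about 8%. Combining the sexes in one coefficient is itself inferred from the absence of strata, not stated. All of this stands, and it makes the point conditional.

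The study is also a declared exploratory pilot. At n = 10 neither coefficient can establish or refute a link, the SAP already asks for a 95% interval, and the female-male comparison would reveal a sex difference in signal. This limits the importance of the point. It does not remove it: the SAP applies the 0.05 level to all analyses, an interval around a confounded coefficient is centred on the wrong quantity for a signal-function claim, and the female-male comparison does not cover walk distance.

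A crude association is a legitimate description, and with one or two volunteers of one sex the adjustment rests on very little. That stands too, and is why the crude coefficient should stay beside the adjusted one.

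Finally, clustering of locations may be the larger source of false correlation here (step 5). That is a separate issue, but any remedy has to fix the unit of analysis first.

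**Conclusion.** The point holds in conditional form and is minor. The plan has no safeguard against a sex contrast appearing as a signal-function correlation. The distortion needs a sex difference in both variables: it is negligible at 0.5 SD in each, modest at 1 SD (8.7% against 5%) and material from about 1.5 SD (19%, rising to 37% at 2 SD, 5/5 split). These rates rest on assumed differences, one value per volunteer and no within-sex relation. Only sex was simulated; height would act by the same mechanism.

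A reader might infer that the plan's correlation will be spurious, or that the protocol expects the signals to differ by sex. The documents support neither: they list a comparison between women and men and give no figure. Nor does the point reach the primary before/after comparison.

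**What to change.** Add a short paragraph to the SAP for these two objectives:

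- Use one value per volunteer for each signal, say how it is formed, and state that this departs from treating anatomical locations as independent.
- Report the partial correlation with 6-MWT distance given sex (Pearson, or computed on ranks where Spearman applies), with its 95% interval, beside the crude coefficient.
- Mark the plotted points by sex.
- Add height as a sensitivity analysis.
- Do not interpret a crude correlation as a signal-function link if it is not also seen after adjustment, and label the result descriptive.

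No new data are needed, and SPSS, already named in the SAP, computes partial correlations. The cost is one degree of freedom (critical |r| 0.632 to 0.666; 0.707 if height is added to sex) and a slightly wider interval. The adjusted value carries little information if one sex has only one or two volunteers; the report should then give the split and say so.

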***Study type***

Since no data exists to date to support the hypothesis of this study, this is an exploratory study.

## 7. Target parameters

All measurements with MSOT are performed at three muscle positions of the proximal and distal lower extremity muscles in lateral comparison (right - left, leg proximal: Musculus quadriceps, distal: Musculus gastrocnemius) by two different examiners, in healthy subjects, at two different timepoints.

### **Primary target:**

Quantitative hemo/myoglobin and collagen signal (in arbitrary units)

*This target is measured non-invasively by MSOT.*

### **Secondary targets:**

Quantitative lipid signal (in arbitrary units)

Muscle oxygenation (in arbitrary units)

*This target is measured non-invasively by MSOT.*

6-minute walk test (6-MWT)

*This target value is clinically determined at presentation.*

Age

Gender

Weight

Skin colour

Ethnic background

Underlying diseases

Current medication

*This information is collected for the study at presentation.*

## **8. Study design**

### **Monocentric / multicentric**

This is a monocentric study with prospective data acquisition (Investigator Initiated Trial, IIT).

### **Study arms: intervention/control**

Interventions are not planned. A comparison is made between healthy volunteers. The study procedure is identical for all test subjects.

[figure not shown]
### **Randomization**

Randomization is not planned. There is no allocation to groups.

### **Blinding**

Blinding for the study is not possible due to the study design. Blinding is performed during the measurement and analysis of the data. Blinding of the test subjects is not necessary.

## Graphical presentation of study design

## 9. Study population

### **Inclusion and exclusion criteria**

#### ***Inclusion criteria:***

Healthy volunteers:

- Adult (>18 years of age) participants

#### ***Exclusion criteria:***

Participants:

- anamnestic or other signs of myopathy
- pregnancy
- Tattoo on skin to be examined
- missing consent form

### **Participant number**

As this is a pilot study, it is not possible to calculate the exact number of cases. It is planned to examine a total of 10 healthy volunteers.

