## 12. Biometrics

### **Explorative study: explanation of the statistical methodology, justification of the selected number of cases**

#### ***Case number calculation:***

As this is a pilot study and no information on the expected differences between the different groups is available yet, no case number calculation was performed. The number of cases given represents an estimate.

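### Two secondary objectives compare women with men, but the recruitment text does not secure both sexes and the SAP prespecifies no between-person test

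*Protocol*

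**What the plan says.** Protocol section 6, under secondary objectives, contains two comparisons by sex. One covers "hemo/myoglobin and collagen signal determined by MSOT in muscle tissue of healthy female and male volunteers". The other reads "Comparison of the quantitative proportion of oxygenated and deoxygenated hemo/myoglobin signals determined by MSOT in muscle tissue of healthy female and male volunteers". Section 7 lists gender among the data recorded at presentation, so the two groups can be formed if both sexes enrol.

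Section 9 sets one inclusion criterion, "Adult (>18 years of age) participants". Its exclusions concern myopathy, pregnancy, tattoos over the examined skin and missing consent. On numbers it says "It is planned to examine a total of 10 healthy volunteers", and the recruitment paragraph does not mention sex. Section 12 adds that "The number of cases given represents an estimate", and the SAP says "Therefore, no sample size calculation was performed".

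For two sets of values the SAP states: "MSOT signals are compared matched manner using a paired t-test when parametric and a Wilcoxon matched-pair signed rank test when non-parametric". It reserves ANOVA and the Friedman test for three or more groups. The t-test in protocol section 12 is tied to timepoint 1 versus timepoint 2. The SAP also declares all anatomical locations independent, and it averages where several scans exist.

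**The concern.** A comparison of women with men needs two things that the plan does not supply.

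The first is enough people of each sex. Under section 9 a sample of 8:2, 9:1 or 10:0 complies fully with the protocol, so the precision of the two objectives is left to chance in recruitment.

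The second is an analysis for unrelated people. Women and men form no natural pairs, and a matched test cannot be set up at all when the group sizes differ. The analyst would have to choose a method after the data are in. If that choice kept the SAP's independence rule, several values from one person could be analysed as if they came from several people.

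The protocol's benefits section says the quantified differences may help to plan later studies. A sex difference with a badly unbalanced sample or an overstated precision would not serve that purpose.

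**Working it through.** **Inputs.** The total is 10 (protocol section 9). The documents give no SD, expected difference, power or sex ratio, so there is no sample-size figure to reproduce, and results are in units of the between-volunteer SD. Two assumptions are mine: equal variances for the half-widths (8 degrees of freedom, t = 2.306), and the sex ratio of the recruitment pool.

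**Precision by split.**
- SE relative to 5:5 = √[(1/n₁ + 1/n₂) / 0.4], where 0.4 = 1/5 + 1/5.
- 95% half-width in SD = 2.306 × √(1/n₁ + 1/n₂). At 5:5 this is 2.306 × 0.632 = 1.46.
- Smallest exact two-sided Mann-Whitney p = 2 / C(10, n₁). At 9:1 this is 2/10 = 0.20.

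| Split | SE vs 5:5 | 95% half-width (SD) | Smallest Mann-Whitney p |
|---|---|---|---|
| 5:5 | 1.00 | 1.46 | 0.008 |
| 6:4 | 1.02 | 1.49 | 0.010 |
| 7:3 | 1.09 | 1.59 | 0.017 |
| 8:2 | 1.25 | 1.82 | 0.044 |
| 9:1 | 1.67 | 2.43 | 0.20 |
| 10:0 | no estimate | no estimate | no test |

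At 9:1 a Mann-Whitney test can never reach the SAP's 0.05. A Welch test is not available either, because one person gives no variance.

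**Chance of each split, assuming a 50:50 pool.** Binomial(10, 0.5):
- 7:3 or worse: 2 × (1 + 10 + 45 + 120) / 1024 = 34.4%
- 8:2 or worse: 2 × (1 + 10 + 45) / 1024 = 10.9%
- 9:1 or worse: 2 × (1 + 10) / 1024 = 2.1%
- all one sex: 2 × 1 / 1024 = 0.2%

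**If the pool is uneven (assumed ratios).**

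| Pool | Rarer sex has 2 or fewer | All one sex |
|---|---|---|
| 70:30 | 38.4% | 2.8% |
| 80:20 | 67.8% | 10.7% |
| 90:10 | 93.0% | 34.9% |

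**Counting sites as people.** Protocol section 10 gives 3 positions × 2 muscles × 2 sides = 12 sites per volunteer, or 120 site values from 10 people at each examination. In a comparison between people, treating k sites as independent understates the standard error by a factor of √[1 + (k − 1)ρ], where ρ is the within-person correlation. The documents do not give ρ. The factor runs from 1 (ρ = 0) to √12 = 3.46 (ρ = 1) over all sites, and up to √6 = 2.45 within one muscle.

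**What balance achieves.** At 5:5 an unpaired t-test has 80% power only for a difference of 2.02 SD, and 29% power for a difference of 1 SD (two-sided 0.05).

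**The case against.** The strongest reply is that sex is peripheral here. None of the listed hypotheses mentions it, and the study is declared an exploratory pilot with no sample-size calculation. The SAP's own list of contrasts is examiner, exercise, time, muscle and muscle position. Those contrasts are repeated measurements on the same volunteers, so the matched-test sentence can fairly be read as written for them.

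Much of this stands. A reader might infer that the SAP prescribes a matched test for women versus men and so a meaningless p value. The documents do not support that: sex is absent from the SAP's list, and the fair statement is that no valid test is prespecified. The omission remains, because the protocol keeps the two objectives and no other sentence covers them.

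A second reply is that a 10:0 sample is very unlikely with a balanced pool, and that most of the 34% is 7:3 itself, where the loss is only 9%. That is correct. The less favourable pools above are assumptions. The recruitment paragraph says only that volunteers will be told about the study, and nothing in it shows that recruitment would be skewed.

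Third, the protocol's design figures are not in the text available for this review and might show a planned split. If so, the participant-number text should match them. The statement that "There is no allocation to groups" concerns randomization and does not settle the matter.

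**Conclusion.** The point holds as a low-cost improvement to two secondary objectives. The recruitment text does not secure both sexes, and neither document prespecifies a between-person analysis for the comparison.

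The loss of precision is small at 7:3 (9%), moderate at 8:2 (25%) and large at 9:1 (67%). The chances of 34%, 11% and 0.2% for 7:3 or worse, 8:2 or worse and all one sex rest on an assumed 50:50 pool. The missing analysis rule matters at every split.

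Two stronger conclusions are not supported. The comparison is not likely to be impossible unless recruitment is strongly skewed. Nor does a 5:5 split make it conclusive: a half-width of about 1.46 SD, which assumes equal variances, leaves it descriptive. Low power alone is no fault in a pilot that makes no claim to it.

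**What to change.** **Protocol section 9, participant number.** Plan 5 female and 5 male volunteers, and close enrolment for a sex once its 5 places are filled. The total stays at 10. The cost is slightly slower recruitment if one sex fills first.

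**SAP.** Add a short rule that takes the female-male comparison out of the matched-test and independent-locations rules:
- For each muscle, calculate one mean per volunteer from the pre-exercise scans at timepoint 1, over positions, sides, examiners and repeat scans. Keeping to the pre-exercise state avoids mixing conditions between which the protocol expects hemo/myoglobin to differ.
- Compare the sexes with a Welch t-test or a Mann-Whitney test, with the choice stated in advance.
- Report the difference with its 95% interval and label the result descriptive.

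No further measurements are needed. If the sponsor does not want to plan for sex, removing the two objectives would also resolve the inconsistency.
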